5.1. Sample Size

By assuming an 80% power with one-sided alpha of 2.5%, the win ratio methodology is applied to the primary endpoint that consists of five components. The required sample size is 432 subjects (216 subjects per arm); and planning for follow up attrition and further describing secondary endpoints/exploratory analysis, the study will enroll up to a total of 550 randomized subjects (RCT Cohort). The "event" proportions of the five components are based on Inari sponsored studies and a review of literature.

Up to 150 additional subjects who meet all eligibility criteria and who have an absolute contraindication to thrombolytics, whose initial planned primary treatment strategy includes FlowTriever, will be enrolled as part of the Contraindication Cohort. The same clinical assessments and follow up schedule will be administered in this cohort as is described for the RCT Cohort.

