where $D_i = 1$ for subjects in FlowTriever arm and $D_i = 0$ for subjects in CDT arm, and N is the number of total subjects in the trial. The proposed F-S statistic for the hypothesis of interest is T / \sqrt{V} , where $V = \frac{n_{FT} n_{CDT}}{N(N-1)} \sum_i U_i^2$ is the variance of T , n_{FT} and n_{CDT} are the number of subjects in FlowTriever and CDT

PROPRIETARY AND CONFIDENTIAL

The information contained in this document is the sole property of Inari Medical

	PEERLESS Study: Statistical Analysis Plan	Version 5.0 March 22, 2024 Page 17 of 25
---	--	--

arms, respectively, and $n_{FT} + n_{CDT} = N$. The hypothesis is tested by comparing the F-S statistic to the standard normal distribution (Finkelstein & Schoenfeld⁴).

To determine the sample size required to achieve 80% power given one-sided alpha of 2.5%, we first will simulate subject level data per data replicate. For a data replicate and within a treatment arm, clinical outcomes with event proportions are sampled from binomial distribution; ICU is from a multinomial distribution with 3 categories, including no ICU admission, ≤ 24 hours, and > 24 hours. We will assume each of the clinical outcomes are independent of each other. For example, we may sample 100 subjects per treatment arm, and within each treatment arm each has different clinical outcome proportions or means. Once we generate 200 subjects in total (100 per treatment arm), we may derive the F-S test statistic and its p-value. We will then repeat the process for 2,500 data replicates and derive 2,500 p-values based on F-S test statistics; power is the proportion of p-values that are ≤ 0.05 . Each given sample size number will thus lead to one power number to be calculated. As we alter the sample sizes in the simulation scenario, we can conduct a grid search to determine the minimal sample size required to achieve at least 80% power.

The primary and secondary endpoints will be analyzed for both ITT and PP populations, separately. Primary endpoint and secondary endpoints will lead to hypothesis testing whereas, only descriptive summary statistics will be provided for the Contraindication Cohort.

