5.4. Secondary Endpoints Analysis

5.4.1. Composite Endpoint of Four Clinical Events

Similar to the primary endpoint for this study, the composite clinical endpoint constructed as a win ratio hierarchy of the four components (see section 2.6) will be assessed using the F-S statistic with the following null and alternative hypotheses:

$$H_0: n'_{FW} \leq n'_{CW} \text{ versus } H_A: n'_{FW} > n'_{CW}$$

where n'_{FW} is the random variable of the number of winners for the FlowTriever System (i.e., counting the number of pairs in which the subject i in FlowTriever System does better than those in CDT arms) while n'_{CW} is the random variable of the number of winners for CDT (i.e., counting the number of pairs in which the subject i in FlowTriever System does worse than those in CDT arms). Additionally, the 95%CI of the win ratio of the treatment effect of this endpoint will be presented.

This composite endpoint will be assessed in both ITT and PP populations. If the results of the ITT and PP populations are similar, it indicates robust confidence on the treatment effect of FT relative to CDT.

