5.5. Exploratory Analysis

Exploratory analysis may be, but not limited to, performed on additional outcomes of interest with descriptive statistics and hypothesis testing. The same approach described in Section 5.6 will be applied to control for overall α . Continuous variables will report any combination of mean, SD, median, Q1, Q3, IQR, minimum and maximum, while the categorical variables will report frequency count and percentages (%).

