5.6. Controlling for Multiplicity

For the primary and secondary endpoints related to safety, α is set to 0.05, to conservatively include all potential safety signals. The secondary endpoints listed below are considered as safety endpoints:

- Composite clinical endpoint constructed as a win ratio hierarchy of the following four components, assessed at hospital discharge or at 7 days after the index procedure, whichever is sooner:
 - All-cause mortality, or
 - Intracranial hemorrhage (ICH), or
 - Major bleeding per ISTH³ definition, or
 - Clinical deterioration defined by hemodynamic or respiratory worsening, and/or escalation to a bailout therapy
- Four Individual components of the win ratio composite endpoint, assessed at hospital discharge or at 7 days after the index procedure, whichever is sooner:
 - All-cause mortality
 - Intracranial hemorrhage (ICH)
 - Major bleeding per ISTH³ definition

PROPRIETARY AND CONFIDENTIAL

The information contained in this document is the sole property of Inari Medical

	PEERLESS Study: Statistical Analysis Plan	Version 5.0 March 22, 2024 Page 24 of 25
---	--	--

- Clinical deterioration defined by hemodynamic or respiratory worsening, and/or escalation to a bailout therapy
- All-cause mortality within 30 days from index procedure
- PE-related and all-cause readmission within 30 days from index procedure
- Device and drug-related serious adverse events through the 30 day visit
- Clinically Relevant Non-Major (CRNM) and Minor bleeding events through hospital discharge or at 7 days after the index procedure, whichever is sooner

For the secondary endpoints not related to safety, the family-wide type I error rate will be controlled at one-sided $\alpha=0.025$ using the Bonferroni correction with an effective number of independent tests. The typical Bonferroni correction assumes all tests are independent and is therefore extremely conservative. An alternative approach to estimate the effective number of independent tests for the correlated tests has been proposed by Gao et al (2008)⁹. Therefore, the α to adjust for multiplicity is simply

$$\frac{\text{familywide type I error}}{\text{effective number of independent tests}}$$

The secondary endpoints listed below are considered as non-safety endpoints:

- ICU admission and ICU length of stay post index procedure and following the index procedure
- Change in right-ventricular/left-ventricular (RV/LV) ratio from baseline to 24 hour visit, as measured by echocardiography or CT

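### Ten FlowTriever-superiority tests labelled as safety are each run at an unadjusted alpha of 0.05, and no secondary test depends on the primary result

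*SAP*

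**What the plan says.** SAP 5.2 makes the secondary endpoints formal tests: "Primary endpoint and secondary endpoints will lead to hypothesis testing". SAP 5.6 then sets the error rates for two groups.

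- Primary and safety-labelled secondaries: "For the primary and secondary endpoints related to safety, α is set to 0.05, to conservatively include all potential safety signals". No adjustment follows, and the text does not say whether 0.05 is one-sided or two-sided.
- Non-safety secondaries: "For the secondary endpoints not related to safety, the family-wide type I error rate will be controlled at one-sided" 0.025, by Bonferroni with an effective number of independent tests.

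The list introduced by "The secondary endpoints listed below are considered as safety endpoints" includes death, intracranial hemorrhage (ICH) and major bleeding. It also includes what SAP 5.4.1 calls "the composite clinical endpoint constructed as a win ratio hierarchy of the four components", which is the primary endpoint without its ICU tier.

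SAP 5.5 allows an open-ended set of exploratory tests and adds: "The same approach described in Section 5.6 will be applied to control for overall" alpha. Neither the SAP nor the protocol makes any secondary test conditional on the primary. The protocol's statistics section contains no multiplicity scheme.

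**The concern.** The reason given for leaving the safety group unadjusted is that potential safety signals should not be missed. That is sound for a test that looks for harm: a looser threshold raises more alarms, and a false alarm is the cautious error. The hypotheses in SAP 5.4 point the other way. Each alternative says that FlowTriever has more wins or fewer events, so a rejection supports superiority and cannot reveal harm from FlowTriever. For such a test a looser threshold is liberal.

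The plan therefore adjusts dyspnea scores, length of stay and quality of life, and leaves unadjusted the comparisons with most clinical weight: death, ICH, major bleeding, deterioration or bailout, and the four-component win ratio. Because nothing is tied to the primary, a nominally significant result on any of these could be presented as a benefit after a failed primary. The documents would offer no error rate for that statement.

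**Working it through.** **Plan's own figure.** SAP 5.1 gives 432 subjects (216 per arm) for the primary: "By assuming an 80% power with one-sided alpha of 2.5" percent. It cannot be reproduced, because the component event proportions are not given. The point does not depend on it. The plan states no familywise error for the safety group.

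**Counting the tests.** Safety-labelled endpoints with a test in SAP 5.4:

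1. Four-component composite (5.4.1), Finkelstein-Schoenfeld (F-S) test
2. Death by discharge or day 7 (5.4.2)
3. 30-day death (5.4.3)
4. ICH (5.4.4)
5. Major bleeding (5.4.5)
6. Deterioration or bailout (5.4.6)
7. PE-related readmission (5.4.8)
8. All-cause readmission (5.4.9)
9. Clinically relevant non-major (CRNM) bleeding (5.4.10)
10. Minor bleeding (5.4.11)

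Numbers 2 to 10 use Fisher's exact test. All ten alternatives favour FlowTriever. Device- and drug-related serious adverse events are on the safety list but have no test in 5.4, so they are not counted.

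**Upper reference.** For ten independent tests of exact size, the chance of at least one false rejection is 1 − (1 − α)^10:

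- α = 0.025: 1 − 0.975^10 = 22.4%
- α = 0.05: 1 − 0.95^10 = 40.1%

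**Simulation.** The real figure is lower, because Fisher's test is conservative for rare events and the ten tests overlap. Trials were simulated with no difference on any endpoint. In the first six rows below, death by day 7 was nested in 30-day death, PE readmission in all-cause readmission, and ICH counted as major bleeding (the major-bleeding entry is before ICH is added). Latent correlation between outcomes was 0 to 0.6 in rows 2, 4 and 6, and 0 to 0.3 in rows 1, 3 and 5. Replicates per setting were 3,000 (rows 2, 4, 6) or 8,000 (rows 1, 3, 5). The last two rows come from a separate simulation of 4,000 trials. The F-S statistic was computed with the variance formula in SAP 5.2.

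All event rates are assumptions. The documents bracket some of them. The protocol's FLASH interim results report 1.3% major bleeding, no deaths at 48 hours and 0.5% mortality at 30 days. Its summary of the meta-analysis of thrombolysis catheters reports major bleeding of 4% with ultrasound-assisted and 10% with conventional catheters.

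Rates in %, in the order: 7-day death / 30-day death / ICH / major bleeding / deterioration / PE readmission / all readmission / CRNM / minor.

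| Assumed rates | Per arm | One-sided 0.025 per test | One-sided 0.05 per test |
|---|---|---|---|
| 0.1/0.5/0.1/1.3/2/0.5/5/2/3 | 275 | 7.4-7.7% | 15.1-15.4% |
| 0.5/1/0.3/3/3/1/5/3/5 | 216-275 | 7.0-9.1% | 14.5-18.9% |
| 2/3/0.5/4/4/1/5/6/10 | 275 | 10.4-11.3% | 21.1-22.8% |
| 2/3/0.5/7/5/2/8/7/10 | 216-275 | 9.3-11.9% | 18.2-22.6% |
| 4/6/1/10/10/5/10/10/12 | 275 | 12.4-13.9% | 24.0-26.1% |
| 4/6/1.5/10/10/5/12/12/20 | 216-275 | 11.1-14.3% | 20.5-27.1% |
| 1/2/0.5/4.5/5/1/6/6/12 | 275 | 11.3% | 22.4% |
| 3/5/1/9/10/2/10/10/20 | 275 | 14.6% | 27.0% |

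The simulation standard error is below one percentage point; for example, √(0.27 × 0.73/3,000) = 0.8 points. The one-sided 0.025 column is the one that applies if the 0.05 in SAP 5.6 is two-sided.

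**Repeat in the per-protocol population.** SAP 3.2 repeats every test there. This is not counted. If a result in either population could be claimed, the error could only rise.

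**The case against.** The strongest reply is that SAP 5.6 prespecifies this choice openly, that its caution concerns catching safety signals, and that nowhere do the documents say a single significant safety-labelled test will be claimed as superiority. The last part stands: a reader might infer that the sponsor plans such claims, and the text does not show it. But the SAP writes each test as a superiority hypothesis and nowhere calls the p-values nominal. In 5.4.1 it treats agreement between the two populations as support for a treatment effect of FlowTriever on the composite. The intended use is therefore open, which is why a wording change is needed.

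Three stronger readings are also tempting.

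- A reader might infer that the safety label is what frees these tests from a gate on the primary. It is not: the non-safety family has no gate either. The label removes only the Bonferroni adjustment.
- A reader might quote 22% or 40% as the error rate. Those figures need independent tests of exact size. Here the composite contains four of the other tests and other endpoints are nested, so they serve only as upper references.
- A reader might conclude that the SAP 5.5 approach could never control error for exploratory tests. Bonferroni with an effective number of tests can be applied to any defined set. What fails is the word overall: 5.6 leaves ten listed secondaries outside any control, and 5.5 defines no family.

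**Conclusion.** The structural point holds on the text alone: ten formally tested, one-sided FlowTriever-superiority hypotheses, each at an unadjusted 0.05, and no secondary in either group conditional on the primary. The statement in SAP 5.5 that the 5.6 approach controls overall alpha is not true of that scheme.

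The size rests on assumptions. With 216 to 275 per arm and the event rates tabulated above, the chance of at least one false FlowTriever benefit among the ten is roughly 7-15% if 0.05 means two-sided and roughly 15-27% if it means one-sided. The two ranges should not be merged, because the SAP does not settle which applies. Both are for the global null, which is the worst case: if FlowTriever truly reduces some of these events, fewer true nulls remain and the error is lower. In every setting examined it is well above the 2.5% that the plan sets for the non-safety family. The defect remains however the sidedness is resolved. The primary analysis is affected only if 0.05 was meant as one-sided.

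**What to change.** Change the SAP wording as follows.

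- **SAP 5.6, order of claims.** Primary at one-sided 0.025; only if met, the four-component composite at one-sided 0.025; only if that is met, the existing non-safety family at a family-wide one-sided 0.025. With no true effects, the chance of any false claim in this sequence is then at most 2.5%.
- **SAP 5.6, other nine safety-labelled comparisons.** Report confidence intervals and nominal p-values, with no superiority claim. If they are to be confirmatory, put them in one Holm family that either has a stated place in the order relative to the non-safety family or shares its 0.025. Giving both families the full 0.025 would let the error reach about 1 − 0.975² = 4.9% once the primary and composite are truly positive and pass.
- **SAP 5.6, harm.** Keep unadjusted review for harm signals and say that this is its purpose.
- **SAP 5.5.** Call exploratory p-values nominal and delete the claim of overall alpha control.

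**Cost.** The nine comparisons lose stand-alone confirmatory status, or face a stricter threshold under Holm. The composite can no longer be claimed if the primary fails. The non-safety family becomes conditional on two earlier successes. If 0.05 was meant as one-sided, the thresholds for the primary and the composite fall to 0.025, which matches the alpha used for the sample size.

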5.7. Data Poolability Assessment

The planned analysis for this study will pool data by treatment arms across clinical study sites since the study is randomized at the study level and not at the site level; it is possible that certain sites may have heavier proportions of one type of treatment vs the other. Efforts were made to ensure that consistent procedures were used across study sites, including use of the same study protocol, Sponsor monitoring the sites for compliance, and use of identical data-gathering instruments. The appropriateness of pooling the data by treatment arms across sites will be evaluated^{7,8}.

For each treatment arm, it may be necessary to combine two or more low enrolling study sites into pseudo-sites to allow for these analyses. Sites with fewer than six subjects will be ranked by enrollment from low to high. Starting from the lowest enrollment site, sites will be combined into a pseudo site until the combined size reaches the median enrollment among sites. This process will be repeated until all

PROPRIETARY AND CONFIDENTIAL

The information contained in this document is the sole property of Inari Medical

	PEERLESS Study: Statistical Analysis Plan	Version 5.0 March 22, 2024 Page 25 of 25
---	--	--

resulting sites have enrollment equal to or greater than six subjects for each treatment arms. This will be done in a manner to preserve the structure of the study and prevent bias.

Poolability analysis will be performed on the primary endpoint comparing across sites within each treatment arm. Random effects modeling using the inverse variance method will be used to assess heterogeneity between pseudo-sites. This is done by using pseudo-sites as a random effect and further quantifying the heterogeneity in terms of Higgin & Thompson's I^2 index for each arm, where higher I^2 values indicate higher levels of heterogeneity. Poolability analysis will only be performed in the ITT population.

6. Data Handling

Prior to database lock, data extracts may be provided to an unblinded member of the Biostatistics and Programming team. The unblinded team member is responsible for masked treatment assignments prior to handing the data over to the blinded Biostatistics and Programming team. Details of the masking process are provided in the Data Masking Plan.

7. References

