5.3. Primary Endpoint Analysis

The primary endpoint for this study will be assessed using the F-S statistic with the following null and alternative hypotheses:

$$H_0: n_{FW} \leq n_{CW} \text{ versus } H_A: n_{FW} > n_{CW}$$

where n_{FW} is the random variable of the number of winners for the FlowTriever System (i.e., counting the number of pairs in which the subject i in FlowTriever System does better than those in CDT arms) while n_{CW} is the random variable of the number of winners for the CDT (i.e., counting the number of pairs in which the subject i in FlowTriever System does worse than those in CDT arms).

To separately quantify the treatment effect of interest, the win ratio of the treatment effect is defined by Pocock et al.⁵, where the performance differences between the two treatment arms is defined as $\frac{N_{FW}}{N_{CW}}$, where N_{FW} is the number of winners for the FlowTriever System and N_{CW} is the number of winners for CDT in the dataset; the 95% CI of the win ratio estimate can be derived via a bootstrap method, a method whereby the original data is sampled with replacement with a large number of times, e.g. 1000 samples being drawn to create 1000 datasets. From each bootstrap sample, the win ratio of the treatment effect is computed and an empirical distribution of the win ratio is determined from the total number of sample datasets. The lower and upper limits of the 95% CI are the 2.5%ile and 97.5%ile

PROPRIETARY AND CONFIDENTIAL

The information contained in this document is the sole property of Inari Medical

	PEERLESS Study: Statistical Analysis Plan	Version 5.0 March 22, 2024 Page 18 of 25
---	--	--

of this empirical distribution of the win ratio out of 1000 samples. In this study, FT and CDT groups are labelled **F** and **C** with n_F and n_C subjects, respectively. The following are the five steps of calculating 95% CI via a bootstrap approach:

1. Draw a random sample S_F of size N_F (275) with replacement from the original FT group and a random sample S_C of N_C with replacement from original CDT group. In this study, $S_F = S_C$.
2. Perform the unmatched analysis, all possible pairs comparison, on the samples S_F , S_C and calculate the win ratio of the treatment effect.
3. Repeat Steps 1 and 2 1000 times.
4. Determine the empirical bootstrap distribution of the win ratio from the 1000 bootstrap values.

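### The poolability analysis measures site differences in outcome level within each arm and does not estimate whether the FlowTriever-versus-CDT effect varies by site

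*SAP*

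**What the plan says.** SAP 5.7 starts from the decision to pool: "The planned analysis for this study will pool data by treatment arms across clinical study sites". Randomisation is at study level, and the section accepts that "it is possible that certain sites may have heavier proportions of one type of treatment vs the other". It promises to evaluate whether pooling is appropriate, and the evaluation is this: "Poolability analysis will be performed on the primary endpoint comparing across sites within each treatment arm". The model is given as "Random effects modeling using the inverse variance method will be used to assess heterogeneity between pseudo-sites", and the summary is an "I^2 index for each arm, where higher I^2 values indicate higher levels of heterogeneity". Small sites are merged until all "resulting sites have enrollment equal to or greater than six subjects for each treatment arms".

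The section gives no I-squared cut-off and no consequence of a high value. It also does not say which within-arm summary of the primary endpoint, or which variance, enters the inverse-variance weights.

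The pooled data serve a comparison between arms. SAP 5.3 introduces the win ratio with the words "where the performance differences between the two treatment arms is defined as", followed by the ratio of FlowTriever wins to CDT wins. The F-S test in SAP 5.2 and the bootstrap in 5.3 do not use site. Neither document plans a treatment-by-site term, a site-level win ratio or a site-stratified F-S test.

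**The concern.** The reason to ask about pooling is that the treatment contrast might not be the same everywhere. I-squared across sites within one arm answers another question: whether that arm's patients fare differently from site to site. Here such differences are expected. The fifth component is ICU admission and stay, and the protocol's ICU definition extends to comparable high-acuity floors. CDT follows local practice, and its dose and duration are left to investigator discretion and local standards. Up to 60 sites will differ in level, and a difference that is common to both arms does not by itself argue against pooling a randomised contrast.

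Effect variation is also plausible. A site that sends both arms to the ICU for similar times will show little difference on this component. The planned statistic does not estimate such variation. At stake is the poolability statement: ordinary practice variation could be reported as doubt about pooling, or low per-arm values as reassurance about a contrast that was never examined.

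**Working it through.** SAP 5.7 states no figure, so there is none to reproduce. The check is whether per-arm I-squared can stand in for I-squared of the treatment effect.

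**Inputs from the documents.** Up to 550 subjects at up to 60 sites (SAP 2.1), and at least six subjects per arm in each pseudo-site (SAP 5.7). 550/60 = 9.2 subjects per site, or 4.6 per arm, so at the full number of sites the average site falls short of six per arm. 275/6 = 45.8, so at most 45 pseudo-sites are possible. Two layouts were used: 25 pseudo-sites with 11 per arm (25 × 22 = 550) and 40 with 7 per arm (40 × 14 = 560, slightly above the maximum).

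**Assumed inputs.** The documents give no outcome rates and no between-site SDs. All those below are assumptions, with SDs from 0.5 to 1.5 on the logit scale.

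**Step 1: variance components.** τ²(effect) = τ²(FT) + τ²(CDT) − 2 cov(FT, CDT). The SAP looks at the first two terms only.
- Same effect everywhere, shared site SD 1.0: 1 + 1 − 2 = 0.
- Arms vary in opposite directions, SD 0.5 each: 0.25 + 0.25 + 0.5 = 1.
- Only CDT varies, SD 1.0: 0 + 1 − 0 = 1.

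**Step 2: expected I-squared by hand.** I² ≈ τ²/(τ² + s²). For a binary ICU outcome near 50%, the logit sampling variance per arm is s² = 1/(0.25n), which is 0.571 at n = 7 and 0.364 at n = 11. For the effect it is 2s².
- Same effect, SD 1.0: per arm 1/1.571 = 64% (n = 7) or 1/1.364 = 73% (n = 11); effect 0%.
- Opposite directions, SD 0.5: per arm 0.25/0.821 = 30% or 0.25/0.614 = 41%; effect 1/2.143 = 47% or 1/1.727 = 58%.

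**Step 3: simulation with F-S scores.** 40 pseudo-sites, 7 per arm, three ICU categories, pooled within-site variance.

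| Scenario | Median I²: FT / CDT / effect |
|---|---|
| Same effect, site SD 1.0 | 64% / 64% / 1% |
| Same effect, site SD 1.5 | 78% / 78% / 4% |
| Effect SD 1.0, no baseline variation | 64% / 0% / 44% |

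Across other assumed rates, the first scenario gives about 60–75% per arm and about 0–15% for the effect.

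**Step 4: simulation with a binary stand-in.** ICU admission at 50% (FT) and 73% (CDT), each site's own variance with 0.5 added to the cells, 2,000 replicates.

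| Scenario | Layout | Median I²: FT / CDT / effect | Q rejects at 5%: FT / CDT / effect |
|---|---|---|---|
| Same effect, site SD 1.0 | 25 × 11 | 48 / 43 / 0% | 90 / 74 / 0% |
| Same effect, site SD 1.0 | 40 × 7 | 26 / 19 / 0% | 41 / 21 / 0% |
| Opposite directions, SD 0.5 | 25 × 11 | 18 / 7 / 38% | 16 / 6 / 61% |
| Opposite directions, SD 0.5 | 40 × 7 | 0 / 0 / 19% | 1 / 0 / 22% |
| Only CDT varies, SD 1.0 | 25 × 11 | 0 / 43 / 32% | 0 / 75 / 45% |
| Arms vary independently, SD 0.5 | 25 × 11 | 18 / 6 / 19% | 16 / 5 / 18% |

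This version is conservative: with no variation at all, Q rejects in 0–1% of replicates. The values are lower than in step 3, but the pattern is the same.

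**Step 5: choice of variance.** With F-S scores and each pseudo-site's own variance, the first scenario in step 3 becomes 82% / 83% / 23%. Under other assumed rates, per-arm values reach 93%, and the effect shows 21–46% although it is constant. Site-specific variances thus inflate I-squared at this size, and the SAP does not say which variance it would use.

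**The case against.** The strongest reply is that SAP 5.7 is descriptive. It sets no cut-off and no action, and the F-S test and win ratio do not depend on it. This stands. A reader might infer that the analysis will flag or clear pooling; the text only allows it to mislead.

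The per-arm method also matches the section's own wording about pooling by arm. Because allocation is not balanced by site and the F-S test is not site-stratified, site differences in outcome bear on chance imbalance and precision. This stands too, so per-arm I-squared is incomplete rather than irrelevant.

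Three further inferences are tempting and not supported.
- That nothing can be computed within one arm because a win ratio needs two. SAP 5.2 scores every subject against all others, so a site mean score within an arm exists, although 5.7 does not name it.
- That pseudo-sites are formed separately by arm and rule out site-level contrasts. The section speaks of combining sites for each arm, but its closing condition can be read as one set with at least six subjects in each arm. It is ambiguous, and sites could be regrouped in any case.
- That per-arm values can never separate practice variation from effect variation. In step 3, reading the arms side by side does separate them: 64/64 against 64/0.

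Finally, an effect I-squared is imprecise at this size and depends on variance and scale. That is true, and it limits the remedy without making the per-arm value a measure of the effect.

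**Conclusion.** The point holds. The only planned poolability evaluation does not estimate the quantity that matters for pooling a between-arm comparison. At an assumed site SD of 1.0 logit, with a constant effect and pooled variances, per-arm I-squared is about 60–75% against about 0–15% for the effect. The binary stand-in gives smaller values (19–48% per arm against 0%) in the same direction.

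The false alarm is the stronger risk. The missed signal needs modest variation in opposite directions; when the arms vary independently, the per-arm and effect values are broadly similar.

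All sizes rest on assumed rates and SDs, while the reading of SAP 5.7 rests on none. A reader might infer that the primary result is compromised. The documents do not support that, since no primary analysis depends on this section.

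**What to change.** Replace the last paragraph of SAP 5.7 and clarify the merging rule:

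1. Form one set of pseudo-sites for both arms together, with at least six subjects per arm in each.
2. In each pseudo-site k, estimate the between-arm effect on one scale named in advance: difference in mean F-S score, net benefit or log win odds. For the score difference, use v_k = s²(FT)/n(FT,k) + s²(CDT)/n(CDT,k), with s² pooled across pseudo-sites within arm.
3. Report Q, τ² and I² of these effects as the poolability result, and say in advance how a high value will be described.
4. Keep per-arm I-squared as description only, naming the summary and variance used.
5. Keep the pooled F-S test as primary. Add a pseudo-site-stratified F-S test as a sensitivity analysis, with pairs formed only within pseudo-site and T and V summed over pseudo-sites.

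The cost is an SAP paragraph and a little programming. Power to detect effect heterogeneity is low at about 9 subjects per site: in the 40 × 7 binary layout, Q detected opposite-direction variation in only 22% of replicates. The SAP should state this, and that a low I-squared does not establish a homogeneous effect. I-squared will also depend somewhat on the effect scale, so the scale should be fixed beforehand.
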